
1. The mandatory Safety Follow-Up visit should be conducted approximately 30 days after the last dose of study therapy or before the initiation of a new treatment, whichever comes first. Patients with an AE of Grade >1 will be further followed until the resolution of the AE to Grade 0-1 or until beginning of a new therapy for their cancer, whichever occurs first.
 
2. Each Follow-Up Visit (FU) has a visit window of \pm 28 days. The first follow-up visit (FU 1) should be scheduled 3 months after the last dose of study therapy. Unless otherwise noted in the flow chart, every effort should be made to collect patient information until (1) 6 months from last dose of pembrolizumab (MK-3475), or (2) the start of a new cancer therapy, whichever occurs first.
 
3. Updated survival status and its respective entry into the database may be requested by the Sponsor at any time during the course of the study. Upon Sponsor notification, all participants who do not/will not have a scheduled study visit or study contact during the Sponsor defined time period will be contacted for their survival status (excluding participants that have a death event previously recorded) (see Section 3.2.5.5).
 
4. Patients who discontinued treatment due to complete response (CR), stable disease (SD), or partial response (PR) will continue to repeat Follow-Up Visit 2 every 3 months until either the end of the study or disease progression. If the patient experiences disease progression, patients will either enter the survival follow-up or have the option to be retreated with pembrolizumab (MK-3475) per the investigator's discretion. Refer to section 3.2.5.4.8
 
5. Vital signs to include temperature, pulse, respiratory rate and blood pressure.
 
6. Collection of all AEs through the 30 day Safety Follow up Visit and SAEs through the FU1 visit (90 days). In patients who start another cancer therapy before 30 days after discontinuation of study therapy, the Safety Follow-Up Visit should occur prior to the patient receiving another cancer therapy. Drug-related AEs should be reported at any time.
 
7. Analysis of T3 or FT4 and TSH will be performed by a central laboratory.
				

8. See appendix 6.1 for a list of laboratory tests.

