3.2.5.4.6 Safety Follow-up Visit

The mandatory Safety Follow-up Visit should be conducted approximately 30 days after the last dose of trial treatment or before the initiation of a new anticancer treatment, whichever comes first. Procedures and assessments performed at the Safety Follow-Up Visit and beyond should follow the respective guidelines described in the Study Flow Chart (Section 1.7) for Parts A, B, C, D, and F as appropriate.

All AEs that occur prior to the Safety Follow-Up Visit should be recorded. Subjects with an AE of Grade >1 will be followed until the resolution of the AE to Grade 0 to 1 or until the beginning of a new anticancer therapy, whichever occurs first. Serious AEs that occur within 90 days of the end of treatment or before initiation of a new anticancer treatment should also be followed and recorded.

Patients who are eligible for retreatment with pembrolizumab (MK-3475) (as described in Section 3.2.5.4.9) may have up to two safety follow-up visits, one after the Treatment Period and one after the Second Course Phase.

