3.4.2 Recording Adverse Experiences

An adverse experience is defined as any unfavorable and unintended change in the structure, function, or chemistry of the body temporally associated with the use of the SPONSOR's product, whether or not considered related to the use of the product. Any worsening (i.e., any clinically significant adverse change in frequency and/or intensity) of a preexisting condition which is temporally associated with the use of the SPONSOR's product, is also an adverse experience.

Changes resulting from normal growth and development which do not vary significantly in frequency or severity from expected levels are not to be considered adverse experiences. Examples of this may include, but are not limited to, teething, typical crying in infants and children, and onset of menses or menopause occurring at a physiologically appropriate time.

Adverse events may occur during clinical trials, or as prescribed in clinical practice, from overdose (whether accidental or intentional), from abuse and from withdrawal.

Progression of the cancer under study is not considered an adverse event.

All adverse events that occur after the consent form is signed but before treatment allocation/randomization must be reported by the investigator if they cause the subject to be excluded from the trial, or are the result of a protocol-specified intervention, including but not limited to washout or discontinuation of usual therapy, diet, placebo treatment or a procedure.

From the time of treatment allocation/randomization through 30 days following cessation of treatment, all serious adverse events and drug related AEOSI must be reported by the investigator. Such events will be recorded at each examination on the Adverse Event case report forms/worksheets. The reporting timeframe for adverse events meeting any serious criteria is described in section 3.4.5.1. The investigator will make every attempt to follow all subjects with non-serious adverse events for outcome.

With Amendment 10, investigators are required to report drug related NSAEs if they meet criteria for AEOSI (refer to the *Pembrolizumab AEOSI Preferred Term List* document) or are ECIs described in Section 3.4.8 below. Previous ECI guidance is now updated in Amendment 10 and is no longer required to be reported to Merck safety group. Other NSAEs do not need to be reported.

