3.4.5.1 Serious Adverse Experiences

A serious adverse event is any adverse event occurring at any dose or during any use of Sponsor's product that:

- Results in death;
- Is life threatening;
- Results in persistent or significant disability/incapacity;
- Results in or prolongs an existing inpatient hospitalization;
- Is a congenital anomaly/birth defect;
- Is an other important medical event

Note: In addition to the above criteria, adverse events meeting either of the below criteria, although not serious per ICH definition, are reportable to the Sponsor in the same timeframe as SAEs to meet certain local requirements. Therefore, these events are considered serious by the Sponsor for collection purposes.

- Is a new cancer (that is not a condition of the study);
- Is associated with an overdose.

Refer to [Table 3-4](#) for additional details regarding each of the above criteria.

For the time period beginning when the consent form is signed until treatment allocation/randomization, any serious adverse event, or follow up to a serious adverse event, including death due to any cause other than progression of the cancer under study (reference Section 3.4.5.1 for additional details), that occurs to any subject must be reported within 24 hours to the Sponsor if it causes the subject to be excluded from the trial, or is the result of a protocol-specified intervention, including but not limited to washout or discontinuation of usual therapy, diet, placebo treatment or a procedure.

For the time period beginning at treatment allocation/randomization through 90 days following cessation of treatment, or 30 days following cessation of treatment if the subject initiates new anticancer therapy, whichever is earlier, any serious adverse event, or follow up to a serious adverse event, including death due to any cause other than progression of the cancer under study (reference Section 3.4.5.1 for additional details), whether or not related to the Sponsor's product, must be reported within 24 hours to the Sponsor either by electronic media or paper. Electronic reporting procedures can be found in the EDC data entry guidelines. Paper reporting procedures can be found in the Investigator Trial File Binder (or equivalent)

Additionally, any serious adverse event, considered by an investigator who is a qualified physician to be related to the Sponsor's product that is brought to the attention of the

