3.5.5.5 Safety Analysis

Safety and tolerability will be assessed by clinical review of all relevant parameters including DLTs, other AEs, laboratory tests, ECG measurements, and vital signs.

DLTs will be listed. At the end of the trial, a dose-response relationship for the rate of experiencing a DLT in Cycle 1 will be estimated using the pooling-of-adjacent-violators algorithm. This dose-safety estimation will be used to support determination of the MTD. The dose-response relationship, overall tolerability and safety profile, and the PK and PD data will inform the determination of a recommended Phase 2 dose.

Note: As of Amendment 11, PK analyses will not be performed (see Section 3.3.2).

The 80% confidence intervals and Bayes credible intervals for DLT and drug-related toxicity rates in Cycle 1 for an identified MTD level will be provided. Summary statistics (median and range) for time to onset of first drug-related toxicity in each dose level will be provided. Adverse experiences will be summarized as counts and frequencies for each dose level. Laboratory assessments, vital signs, and other safety endpoints will be summarized as appropriate.

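### From Amendment 10 the protocol gives two scopes for non-serious AE collection, and the SAP tabulates all AEs by dose level without allowing for the change

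*Combined protocol and SAP*

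**What the plan says.** Section 3.4.2 (Recording Adverse Experiences) sets the narrow scope. From allocation "through 30 days following cessation of treatment, all serious adverse events and drug related AEOSI must be reported by the investigator". From Amendment 10, non-serious events are reported only if they are drug-related AEOSIs or are ECIs under Section 3.4.8; for the rest, "Other NSAEs do not need to be reported". On serious events the same section adds: "The reporting timeframe for adverse events meeting any serious criteria is described in section 3.4.5.1".

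Two other places keep the wide scope. Section 3.2.5.4.6 states "All AEs that occur prior to the Safety Follow-Up Visit should be recorded". The follow-up flow charts in Section 1.7 (footnote 6 for the first course, footnote 7 for the Second Course) say "Collection of all AEs through the 30 day Safety Follow up Visit and SAEs through the FU1 visit (90 days"), and the same footnotes ask for drug-related AEs with no time limit.

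Section 3.4.5.1 sets the SAE window from allocation "through 90 days following cessation of treatment, or 30 days following cessation of treatment if the subject initiates new anticancer therapy, whichever is earlier". Section 3.4.8 uses the same window for ECIs. Section 3.2.5.4.6 words the SAE limit differently: 90 days from the end of treatment, or before new anticancer treatment begins.

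On the analysis side, Section 3.5.3.2 evaluates all other AEs in every part of the study, and Section 3.5.5.5 plans: "Adverse experiences will be summarized as counts and frequencies for each dose level". Neither gives an AE analysis window or mentions the change in collection. Section 3.5 says no separate SAP will be issued. Under Section 1.4, Amendment 10 also put all ongoing patients on 200 mg every 3 weeks.

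**The concern.** Safety and tolerability is the first primary objective (Section 2.1.1). Two sites can each comply with the current protocol and submit different AE data, one with all non-serious events after Amendment 10 and one with almost none. The planned tables would then mix full and restricted collection without saying so.

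The coincidence with the dose change makes this worse. Tables are by dose level, and the restriction starts at the amendment that introduced 200 mg. If 200 mg time is shown as its own level, it has few ordinary non-serious AEs because they were not collected. If it is attributed to the original dose, it adds follow-up with incomplete capture. Second Course treatment after stable disease or partial response, opened by Amendment 10 and given at 200 mg (Sections 1.6 and 3.2.5.4.9), falls wholly in the restricted period.

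Delayed immune-related events are also exposed. Section 3.2.5.4.4 expects that some may arise several months after the last dose, yet the sections disagree on whether a non-serious drug-related AEOSI after day 30 is reported.

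**Working it through.** The plan states no figure that depends on the scope of AE collection, so there is nothing to reproduce. The check is a comparison by event class, followed by an illustration of scale.

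**Comparison of current text**

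| Event class | Section 3.4.2 from Amendment 10 | Other current text | Consistent? |
|---|---|---|---|
| Non-serious, neither AEOSI nor ECI | Not reported | 3.2.5.4.6 and flow charts: all, to the 30-day visit | No |
| Non-serious AEOSI, not drug-related | Not reported | As above | No |
| Non-serious AEOSI, drug-related | To 30 days | Flow charts: no time limit | No |
| ECI | In scope, no window of its own | 3.4.8: 90 days, or 30 with new therapy | Window given only in 3.4.8 |
| SAE, no new therapy | 30-day clause, then refers to 3.4.5.1 | 90 days in 3.4.5.1, 3.2.5.4.6 and flow charts | Yes, through the cross-reference |
| SAE, new therapy started | As 3.4.5.1: 30 days | 3.2.5.4.6: 90 days, or before new therapy | No |

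In the last row, an SAE after day 30 but before the new therapy starts is inside 3.2.5.4.6 and, read literally, outside 3.4.5.1. An SAE within 30 days but after the new therapy starts is inside 3.4.5.1 and, if the earlier limit is meant, outside 3.2.5.4.6. Drug-related SAEs are reportable at any time under 3.4.5.1, so this difference concerns unrelated SAEs.

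**Illustration of scale (assumed inputs)**

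Let q be the share of patients still exposed after Amendment 10, p their true rate of first-onset AEs in that period, and s the share of those AEs that are SAEs, drug-related AEOSIs or ECIs. The documents give none of these. The denominator is the 1260 enrolled (Section 1.5).

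If 3.4.2 is followed, the reported late-period rate is p × s:
- p = 20%: 0.20 × 0.10 = 2%, up to 0.20 × 0.50 = 10%
- p = 50%: 0.50 × 0.10 = 5%, up to 0.50 × 0.50 = 25%

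The understatement of the pooled crude rate is q × p × (1 − s):
- q = 5%, p = 20%, s = 50%: 0.05 × 0.20 × 0.50 = 0.5 points; 1260 × 0.005 = about 6 patients
- q = 10%, p = 20%, s = 10%: 0.10 × 0.20 × 0.90 = 1.8 points; about 23 patients
- q = 30%, p = 50%, s = 10%: 0.30 × 0.50 × 0.90 = 13.5 points; about 170 patients

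The pooled formula assumes that no patient had an earlier event of the same kind; where patients did, the loss is smaller. If sites follow 3.2.5.4.6 instead, nothing is lost up to the 30-day visit.

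**The case against.** A reader might infer that 3.4.2 and 3.4.5.1 conflict on the SAE window, leaving SAEs and AEOSIs uncovered on days 31 to 90. The documents do not support that. Section 3.4.2 sends serious events to 3.4.5.1, which gives 90 days and adds drug-related SAEs at any time. For non-serious AEOSIs no section gives a 90-day limit; the competing text has no limit at all. A 30-day window for AEs beside a 90-day window for SAEs is ordinary tiered collection.

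A reader might also infer that time after Amendment 10 enters a denominator as exposure. Section 3.5.5.5 plans crude counts and frequencies among patients dosed, not exposure-adjusted rates. Only patients whose first event of a kind falls after the change are lost. Table 2-1 shows cohorts enrolled under Amendments 02 to 09 and none under Amendment 10, and Section 3.2.5.6 plans earlier data locks for Parts A and B. The early treatment period therefore largely precedes the restriction. This stands and limits the effect.

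It can be said that recording and reporting differ, or that the Data Entry Guidelines and the AEOSI term list settle the matter. The first does not help: 3.4.2 is itself the section on recording and directs the listed events to the AE case report forms. The second cannot be checked here, so actual confusion at sites is not established. Even so, the contradiction is not leftover wording: the change log shows that Amendment 11 revised both 3.4.2 and 3.2.5.4.6.

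**Conclusion.** The point holds in a limited form. Three things are firm: the scope contradiction for non-serious AEs, the unresolved window for non-serious drug-related AEOSIs, and the absence from the SAP of an AE analysis window or any provision for the change at Amendment 10. The differing SAE cut-off when new anticancer therapy starts is a smaller discrepancy.

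It would go too far to conclude that late AE rates are understated. They may be, where sites follow 3.4.2, and then only for non-serious events outside the retained classes with first onset after the change, and for non-serious drug-related AEOSIs after day 30. Nor does the SAP state a decision to pool across the change; it is silent. The scope restriction leaves SAE rates intact, and Cycle 1 dose-limiting toxicity analyses precede it.

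The size cannot be derived, because the documents give neither the number still on treatment at Amendment 10 nor the mix of late events. The range of 0.5 to 13.5 points shows only how strongly the answer depends on those assumptions.

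**What to change.** 1. Reconcile Sections 3.2.5.4.6, 3.4.2, 3.4.5.1 and 3.4.8 and the flow-chart footnotes so that each event class (ordinary non-serious AE, drug-related AEOSI, ECI, SAE) has one scope and one window, including the cut-off when new anticancer therapy starts.
2. In Section 3.5.5.5, define the AE analysis window. Limit all-AE tables to each patient's period of full AE collection. If the 3.4.2 scope is the one kept, that period ends at the patient's Amendment 10 date; if full collection is kept, no such cut is needed and none should be imposed.
3. Summarise SAEs, drug-related AEOSIs and ECIs separately over the whole study.
4. State how time on 200 mg every 3 weeks, including Second Course treatment, is assigned to dose level.

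The cost is protocol wording and a few SAP sentences, plus a date of transition to Amendment 10 for each patient. If the narrow scope is kept, late ordinary non-serious AEs leave the all-AE tables, and the report should say so. If a wider scope or an open-ended AEOSI window is chosen, sites following 3.4.2 would have more to collect, so that choice is not free.

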3.4.3 Definition of an Overdose for This Protocol

For purposes of this trial, an overdose will be defined as any dose exceeding the prescribed dose for pembrolizumab (MK-3475) by ≥ 1000 mg (5 times the dose). No specific information is available on the treatment of overdose of pembrolizumab (MK-3475). In the event of overdose, pembrolizumab (MK-3475) should be discontinued

and the subject should be observed closely for signs of toxicity. Appropriate supportive treatment should be provided if clinically indicated.

3.4.3.1 Reporting of Overdose to SPONSOR

If an adverse experience(s) is associated with (“results from”) the overdose of test drug or vaccine, the adverse experience(s) is reported as a serious adverse experience, even if no other criteria for serious are met.

If a dose of Sponsor's product or vaccine meeting the protocol definition of overdose is taken without any associated clinical symptoms or abnormal laboratory results, the overdose is reported as a non-serious Event of Clinical Interest (ECI), using the terminology “accidental or intentional overdose without adverse effect.

All reports of overdose with and without an adverse event must be reported by the investigator within 24 hours to the Sponsor either by electronic media or paper. Electronic reporting procedures can be found in the EDC data entry guidelines. Paper reporting procedures can be found in the Investigator Trial File Binder (or equivalent).

3.4.4 Reporting of Pregnancy to SPONSOR

Although pregnancy and lactation are not considered adverse events, it is the responsibility of investigators or their designees to report any pregnancy or lactation in a subject (spontaneously reported to them) that occurs during the trial.

Pregnancies and lactations that occur after the consent form is signed but before treatment allocation/randomization must be reported by the investigator if they cause the subject to be excluded from the trial, or are the result of a protocol-specified intervention, including but not limited to washout or discontinuation of usual therapy, diet, placebo treatment or a procedure. Pregnancies and lactations that occur from the time of treatment allocation/randomization through 120 days following cessation of Sponsor’s product, or 30 days following cessation of treatment if the subject initiates new anticancer therapy, whichever is earlier, must be reported by the investigator. All reported pregnancies must be followed to the completion/termination of the pregnancy. Pregnancy outcomes of spontaneous abortion, missed abortion, benign hydatidiform mole, blighted ovum, fetal death, intrauterine death, miscarriage and stillbirth must be reported as serious events (Important Medical Events). If the pregnancy continues to term, the outcome (health of infant) must also be reported.

3.4.5 Immediate Reporting of Adverse Experiences to the SPONSOR

Any serious adverse experience should be recorded and reported within 24 hours to the SPONSOR via facsimile (found in the administrative binder).

3.4.5.1 Serious Adverse Experiences

A serious adverse event is any adverse event occurring at any dose or during any use of Sponsor's product that:

- Results in death;
- Is life threatening;
- Results in persistent or significant disability/incapacity;
- Results in or prolongs an existing inpatient hospitalization;
- Is a congenital anomaly/birth defect;
- Is an other important medical event

Note: In addition to the above criteria, adverse events meeting either of the below criteria, although not serious per ICH definition, are reportable to the Sponsor in the same timeframe as SAEs to meet certain local requirements. Therefore, these events are considered serious by the Sponsor for collection purposes.

- Is a new cancer (that is not a condition of the study);
- Is associated with an overdose.

Refer to [Table 3-4](#) for additional details regarding each of the above criteria.

For the time period beginning when the consent form is signed until treatment allocation/randomization, any serious adverse event, or follow up to a serious adverse event, including death due to any cause other than progression of the cancer under study (reference Section 3.4.5.1 for additional details), that occurs to any subject must be reported within 24 hours to the Sponsor if it causes the subject to be excluded from the trial, or is the result of a protocol-specified intervention, including but not limited to washout or discontinuation of usual therapy, diet, placebo treatment or a procedure.

For the time period beginning at treatment allocation/randomization through 90 days following cessation of treatment, or 30 days following cessation of treatment if the subject initiates new anticancer therapy, whichever is earlier, any serious adverse event, or follow up to a serious adverse event, including death due to any cause other than progression of the cancer under study (reference Section 3.4.5.1 for additional details), whether or not related to the Sponsor's product, must be reported within 24 hours to the Sponsor either by electronic media or paper. Electronic reporting procedures can be found in the EDC data entry guidelines. Paper reporting procedures can be found in the Investigator Trial File Binder (or equivalent)

Additionally, any serious adverse event, considered by an investigator who is a qualified physician to be related to the Sponsor's product that is brought to the attention of the

investigator at any time following consent through the end of the specified safety follow-up period specified in the paragraph above, or at any time outside of the time period specified in the previous paragraph also must be reported immediately to the Sponsor.

All subjects with serious adverse events must be followed up for outcome.

